#### **8.2.5 Serious Adverse Event Onset and Resolution Dates**

The onset date of the SAE is defined as the date the event meets serious criteria. The resolution date is the date the event no longer meets serious criteria, the date the symptoms resolve, or the date the event is considered chronic. In the case of hospitalizations, the hospital admission and discharge dates are considered the onset and resolution dates, respectively.

In addition, any signs or symptoms experienced by the subject after signing the informed consent form, or leading up to the onset date of the SAE, or following the resolution date of the SAE, must be recorded as an AE, if appropriate.

#### **8.2.6 Fatal Outcome**

Any SAE that results in the subject’s death (ie, the SAE was noted as the primary cause of death) must have fatal checked as an outcome with the date of death recorded as the resolution date. For all other events ongoing at the time of death that did not contribute to the subject’s death, the outcome should be considered not resolved, without a resolution date recorded.

For any SAE that results in the subject’s death or any ongoing events at the time of death, unless another investigational product action was previously taken (eg, drug interrupted, reduced, withdrawn), the action taken with the investigational product should be recorded as “dose not changed” or “not applicable” (if the subject never received investigational product). The investigational product action of “withdrawn” should not be selected solely as a result of the subject’s death.

### **8.2.7 Regulatory Agency, Institutional Review Board, Ethics Committee, and Site Reporting**

The sponsor or the CRO is responsible for notifying the relevant regulatory authorities, US central institutional review boards (IRBs), and European Union (EU) central ethics committees (ECs) of related, unexpected SAEs (ie, SUSARs).

In addition, the CRO is responsible for notifying active sites of all related, unexpected SAEs (ie, SUSARs) occurring during all interventional studies across the ontamalimab program.

The investigator is responsible for notifying the local IRB, local EC, or the relevant local regulatory authority of all SAEs that occur at his or her site as required.

### **8.2.8 Safety Monitoring for Potential Cases of Drug-induced Liver Injury**

The following safety monitoring and stopping criteria are provided for elevated hepatic blood tests based on normal and elevated baseline alanine aminotransferase (ALT) and total bilirubin levels.

Abnormal values in ALT concurrent with abnormal elevations in total bilirubin that meet the criteria outlined below in the absence of other causes of liver injury are considered potential cases of drug-induced liver injury (potential Hy's Law cases) and should always be considered important medical events.

The threshold of laboratory abnormalities for a potential case of drug-induced liver injury depends on the subject's individual baseline values and underlying conditions. Subjects who present with the following laboratory abnormalities per [Table 7](#) should be evaluated further to definitively determine the etiology of the abnormal laboratory values. The measurement(s) should be reconfirmed with another blood draw preferably within 48 to 72 hours of the initial finding of potential concern. Please refer to laboratory manual for further instructions.

Guidance for Dosing Interruption: Investigator-directed delays in dosing due to abnormal laboratory findings or AEs should be discussed with the medical monitor to determine whether the subject should continue with the treatment.

**Table 7 Safety Monitoring Rules for Treatment-emergent Elevated ALT and/or Bilirubin**

Treatment-emergent ALT	Treatment-emergent total bilirubin	Treatment-emergent symptoms	Action

Normal baseline ALT <math>\geq 5 \times</math> ULN
 
Elevated baselinea: ALT <math>\geq 3 \times</math> baseline or <math>\geq 300</math> U/L (whichever occurs first)
	
Normal
 
Patients with Gilbert's syndrome or hemolysis: No change in baseline TBL
	None	
Repeat ALT, AST, ALP, TBL, in 2-5 days.
 
Follow-up for symptoms.
 
Initiate evaluation for other etiologies of abnormal liver tests.
 
Testing for hepatitis A, B, and/or C infection may be warranted. Subjects who entered the induction study (SHP647-301 or SHP647-302) with HBcAb with or without HBsAb would need evaluation with HBV DNA to rule out HBV reactivation.c

Normal baseline ALT <math>\geq 8 \times</math> ULN
 
Elevated baselinea: ALT <math>\geq 5 \times</math> baseline or <math>\geq 500</math> U/L (whichever occurs first)
	
Normal
 
Patients with Gilbert's syndrome or hemolysis: No change in baseline TBL
	None	
Interrupt investigational productb
 
Initiate close monitoring and workup for competing etiologies.
 
Investigational product can be restarted only if another etiology is identified and liver enzymes return to baseline.
 
Testing for hepatitis A, B, and/or C infection may be warranted. Subjects who entered the induction study (SHP647-301 or SHP647-302) with HBcAb with or without HBsAb would need evaluation with HBV DNA to rule out HBV reactivation.c


Normal baseline ALT <math>\geq 3 \times</math> ULN
 
Elevated baselinea: ALT <math>\geq 2 \times</math> baseline or <math>\geq 300</math> U/L (whichever occurs first)
	
TBL <math>\geq 2</math>mg/dL increased over baseline or
 
Patients with Gilbert's syndrome or hemolysis: Doubling of baseline direct bilirubin
	None	
Interrupt investigational productb
 
Initiate close monitoring and workup for competing etiologies.
 
Investigational product can be restarted only if another etiology is identified and liver enzymes return to baseline.
 
Testing for hepatitis A, B, and/or C infection may be warranted. Note: subjects who entered the induction study (SHP647-301 or SHP647-302) with HBcAb with or without HBsAb would need evaluation with HBV DNA to rule out HBV reactivation.c

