**Table 7 Safety Monitoring Rules for Treatment-emergent Elevated ALT and/or Bilirubin**

Treatment-emergent ALT	Treatment-emergent total bilirubin	Treatment-emergent symptoms	Action

Normal baseline            ALT <math>\geq 5 \times</math> ULN
 
Elevated baselinea:            ALT <math>\geq 2 \times</math> baseline or  <math>\geq 300</math> U/L (whichever occurs first)
	Normal or elevated	Severe fatigue, nausea, vomiting, right upper quadrant pain or Immunologic symptoms Rash Eosinophilia $>5\%$	Interrupt investigational product b Initiate close monitoring and workup for competing etiologies. Investigational product can be restarted only if another etiology is identified and liver enzymes return to baseline. Testing for hepatitis A, B, and/or C infection may be warranted. Note: Subjects who entered the induction study (SHP647-301 or SHP647-302) with HBcAb with or without HBsAb would need evaluation with HBV DNA to rule out HBV reactivation. c

ALP=alkaline phosphatase; ALT=alanine aminotransferase; AST=aspartate aminotransferase; HBcAb=hepatitis B core antibody; HBsAb=hepatitis B surface antibody; HBV=hepatitis B virus; TBL=total bilirubin; ULN=upper limit of normal

a Elevated baseline ALT defined as ALT  $\geq 1.5 \times$  ULN.

b Confirmatory repeat liver-related blood tests should be performed within 2-3 days before the investigational product is interrupted.

c If HBV DNA positive, antivirals would need to be started as soon as possible.

Source: Adapted from [Chalasan and Regev, 2016](#).

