Shifts from induction study (SHP647-301 or SHP647-302) baseline category to each visit will be presented by treatment group as listed in Appendix 16.6 for hematology, chemistry, and urinalysis. For hematology and chemistry, shifts will be categorized as Low, Normal, or High. For urinalysis, shifts will be categorized as Abnormal or Normal.

All laboratory data will be listed for the Safety Set.

Table 3: Criteria for Potentially Clinically Important Laboratory Tests

Parameter	Age Range	Sex	Outlier Criteria ^a	
			Low	High
Hematology				
Hemoglobin	All		<8 g/dL	NA
Hematocrit	All		<32%	NA
MCH	All		<LLN	>ULN
MCHC	All		<LLN	>ULN
MCV	All		<LLN	>ULN

Table 3: Criteria for Potentially Clinically Important Laboratory Tests

Parameter	Age Range	Sex	Outlier Criteria ^a	
			Low	High
Erythrocyte (RBC)	All		<3.0 x 10 ⁶ /μL	NA
Leukocytes (WBC)	All		<3.0 x 10 ³ /μL	>20 x 10 ³ /μL
Neutrophils (Abs)	All		<1.5 x 10 ³ /μL	>15 x 10 ³ /μL
Neutrophils (%)	All		<40%	NA
Lymphocytes (Abs)	All		NA	NA
Lymphocytes (%)	All		<10%	>50%
Monocytes (Abs)	All		NA	NA
Monocytes (%)	All		NA	>25%
Eosinophils (Abs)	All		NA	NA
Eosinophils (%)	All		NA	>10%
Basophils (Abs)	All		NA	NA
Basophils (%)	All		NA	>10%
Platelets	All		<75 x 10 ³ /μL	>1,000 x 10 ³ /μL
Chemistry				
Alkaline Phosphatase	All		NA	>2.5 x ULN (or alternatively >400 U/L)
Aspartate Aminotransferase (AST)	All		NA	>2.5 x ULN
Alanine Aminotransferase (ALT)	All		NA	>2.5 x ULN
Total Bilirubin	All		NA	>1.5 x ULN
Total Protein, plasma or serum	All		<5 g/dL	>9 g/dL
Albumin	All		<3 g/dL	NA
Glucose (fasting)	All		<55 mg/dL	>160 mg/dL
Blood Urea Nitrogen (BUN)	All		NA	>2.5 x ULN (or alternatively >29.4 mg/dL)
Creatinine, serum	All		NA	>1.5 x ULN (or alternatively >1.98 mg/dL)
Sodium	All		<130 mEq/L	>150 mEq/L
Potassium, plasma or serum	All		<3 mEq/L	>5.5 mEq/L
Chloride	All		<90 mEq/L	>115 mEq/L
Calcium	All		<8.0 mg/dL	>11.2 mg/dL
Carbon dioxide (NCI uses bicarb)	All		NA	NA
DILI Screen (ongoing safety monitoring)	All		NA	AST or ALT >3 x ULN and TBL >2 x ULN
Urinalysis				
Bilirubin	All		NA	NA
Leukocyte esterase	All		NA	NA
Protein	All		NA	≥2+
Glucose	All		NA	NA

Table 3: Criteria for Potentially Clinically Important Laboratory Tests

Parameter	Age Range	Sex	Outlier Criteria ^a	
			Low	High
Blood	All		NA	NA
Ketones	All		NA	NA
Nitrite	All		NA	NA
pH	All		NA	NA
Specific gravity	All		NA	NA
Urobilinogen	All		NA	NA

LLN=lower limit of normal provided by the laboratory; NA=not applicable; ULN=upper limit of normal provided by the laboratory.

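### Protocol Table 7 assigns no action to an asymptomatic subject with high ALT and moderately raised bilirubin, although the same ALT with normal bilirubin interrupts dosing

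*Protocol*

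**What the plan says.** Protocol Section 8.2.8 presents Table 7 as the study's liver monitoring and stopping criteria. Each row combines an ALT threshold, a bilirubin condition, a symptom condition and an action.

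- **Row 1** (no symptoms): ALT at least 5 times ULN, or at least 3 times baseline or 300 U/L if baseline ALT is elevated. Bilirubin must be normal or, with Gilbert's syndrome or hemolysis, "No change in baseline TBL". The action is repeat testing and work-up.
- **Row 2** (no symptoms): ALT at least 8 times ULN, or at least 5 times baseline or 500 U/L if baseline ALT is elevated. The bilirubin condition is the same as in row 1. The action is "Interrupt investigational product".
- **Row 3** (no symptoms): ALT at least 3 times ULN, or at least 2 times baseline or 300 U/L if baseline ALT is elevated. Total bilirubin must be at least 2 "mg/dL increased over baseline" or, with Gilbert's syndrome or hemolysis, there must be a "Doubling of baseline direct bilirubin". The action is interruption.
- **Row 4**: bilirubin may be "Normal or elevated", but the subject must have symptoms or immunologic signs, such as "Severe fatigue, nausea, vomiting, right upper quadrant pain". The action is interruption.

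The text before the table ties further evaluation to the abnormalities listed in it. It adds that dosing delays directed by the investigator should be discussed with the medical monitor.

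**The concern.** Read together, the first three rows leave a hole. Bilirubin that is no longer normal takes an asymptomatic subject out of rows 1 and 2, but the subject enters row 3 only after a further rise. In between, the table lists nothing, not even the repeat test of row 1.

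This runs against the table's own ordering. It lowers the ALT level for interruption from 8 to 3 times ULN once bilirubin has risen enough, so it treats raised bilirubin as aggravating. Yet at a fixed ALT of 8 times ULN or more, the first part of that rise removes the interruption. A site that follows the table literally would have an instruction for the milder and the more severe picture, and none for the one between. Section 8.2.8 also defines potential Hy's Law cases by the criteria in the table, so a subject in no row falls outside that definition too.

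**Working it through.** The plan gives no figure to reproduce. The check applies the four rows to specified cases.

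**Inputs.** The ALT, bilirubin and symptom conditions come from Table 7. The documents give no bilirubin ULN and no typical baseline. Assumed values are ULN 1.0, 1.2 or 1.5 mg/dL and baseline total bilirubin (TBL) 0.3, 0.6 or 1.0 mg/dL. Row 3 can be read in two ways: (A) a rise of at least 2 mg/dL from baseline, or (B) an absolute value of at least 2 mg/dL that is above baseline.

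**Worked case.** No symptoms, normal baseline ALT, current ALT 10 times ULN, bilirubin ULN 1.2, baseline TBL 0.6.

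| TBL (mg/dL) | Rise | Reading A | Reading B |
|---|---|---|---|
| 0.8 | 0.2 | rows 1 and 2: interrupt | rows 1 and 2: interrupt |
| 1.5 | 0.9 | no row | no row |
| 1.8 | 1.2 | no row | no row |
| 2.0 | 1.4 | no row | row 3: interrupt |
| 2.5 | 1.9 | no row | row 3: interrupt |
| 2.6 | 2.0 | row 3: interrupt | row 3: interrupt |

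If the same subject has row 4 symptoms, row 4 applies at every one of these values.

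**Size of the gap.** Without Gilbert's syndrome or hemolysis, the uncovered band is

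- reading A: ULN < TBL < baseline + 2, width = baseline + 2 − ULN;
- reading B: ULN < TBL < 2, width = 2 − ULN.

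| | ULN 1.0 | ULN 1.2 | ULN 1.5 |
|---|---|---|---|
| A, baseline 0.3 | 1.3 | 1.1 | 0.8 |
| A, baseline 0.6 | 1.6 | 1.4 | 1.1 |
| A, baseline 1.0 | 2.0 | 1.8 | 1.5 |
| B, any of these baselines | 1.0 | 0.8 | 0.5 |

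Widths are in mg/dL. The gap closes only if ULN reaches baseline + 2 (reading A) or 2 mg/dL (reading B), so it is present under every assumption tried.

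**What is lost, by ALT level (normal baseline ALT).**

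- From 3 to below 5 times ULN, the band has no row, but neither does normal bilirubin, so nothing is reversed.
- From 5 to below 8 times ULN, the repeat testing of row 1 is lost.
- From 8 times ULN, the interruption of row 2 is lost.

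**Elevated baseline ALT.** Take ALT rising from 80 to 520 U/L. The baseline counts as elevated if the ALT ULN is at most 80/1.5 = 53 U/L. The rise is 520/80 = 6.5 times baseline, and 520 exceeds 500. Normal bilirubin gives row 2 (interrupt), raised bilirubin short of row 3 gives no row, and bilirubin meeting row 3 gives interruption again.

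**Gilbert's syndrome or hemolysis, ALT at least 8 times ULN, no symptoms.** If total bilirubin is unchanged, row 2 interrupts. If it has changed but direct bilirubin has not doubled, no row applies. If direct bilirubin has doubled, row 3 interrupts.

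**The case against.** The strongest reply is that subjects in the band can still be managed. Section 8.2.8 has a paragraph on dosing interruption that covers delays for any abnormal laboratory finding, not only those in the table, and Section 6.2.3 repeats it. Section 7.3.3.6 allows unexpected values to be repeated. A laboratory shift can be an adverse event (Section 8.1.6), and adverse events can lead to withdrawal (Section 4.5.1). All of this stands. A reader might infer that interruption is barred in the band, and the documents do not say so. But these provisions permit action and assign none, whereas the table assigns one on both sides of the band.

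It could also be said that normal bilirubin in rows 1 and 2 loosely means anything short of row 3. Row 4 tells against that, since its condition "Normal or elevated" separates the two states.

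A second reply concerns exposure, and it stands. A reader might infer from the 12-week spacing of the early laboratory visits that several doses would follow before the next test. Under Amendment 3, however, the next visit is Week 52/ET, due within 4 weeks (±10 days) of the last visit before SHP647-304 Amendment 4, and Table 1 shows no dosing at Visit 14. Little dosing remains in this study for the rule to govern.

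Two further inferences are tempting but not supported.

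- The SAP's Table 3 has a DILI screen, "AST or ALT >3 x ULN and TBL >2 x ULN", which uses AST and a different bilirubin limit. This does not contradict Table 7. Although labelled as ongoing monitoring, it sits among criteria that SAP Section 7.2 uses to count and list subjects, and it sets no interruption rule. Section 8.2.8 also says that its own thresholds depend on the individual baseline, so some difference from a fixed ULN multiple is expected.
- Direct bilirubin is absent from the chemistry lists in Protocol Section 7.3.3.6 and SAP Section 7.2. That does not show that the Gilbert's/hemolysis condition cannot be assessed. Section 8.2.8 refers to a laboratory manual that is not among the documents.

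**Conclusion.** The gap is real and can be read directly from Table 7. An asymptomatic subject with bilirubin above normal but short of row 3 meets no row at any ALT. With Gilbert's syndrome or hemolysis, the same holds when total bilirubin has changed without a doubling of direct bilirubin. At the ALT levels of row 2, the table's response therefore goes from interruption to no listed action and back to interruption as bilirubin rises.

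That conclusion does not depend on how row 3 is read or on any assumed value. Only the width does: 0.8 to 2.0 mg/dL on the rise reading and 0.5 to 1.0 mg/dL on the absolute reading, for the ULN and baseline values assumed above. What is missing is an assigned action, not the possibility of acting.

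The text is current and concerns safety, so it should be corrected. Because Amendment 3 leaves few doses to be given, it is a moderate point and not a critical one.

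**What to change.** The sponsor should reconcile the bilirubin conditions of rows 1 to 3 of Table 7, in the main, elevated-baseline and Gilbert's/hemolysis branches. No asymptomatic combination at or above the ALT thresholds of rows 1 and 2 should be left without an assigned action. The rows need not be mutually exclusive, since their ALT thresholds are nested. The table should also state whether row 3 means a rise of 2 mg/dL or an absolute value. Which action and which threshold apply in the band is for the sponsor to decide.

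Two items need only a check. Confirm, for example in the laboratory manual, that direct bilirubin, including a baseline value, is available for the Gilbert's/hemolysis condition. Add a line to the SAP saying that the DILI screen in Table 3 is a reporting flag whose criteria differ from those of Protocol Table 7.

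The cost is a wording change to one column of one table and a sentence in the SAP. The downside may be a few more repeat tests or interruptions.

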**Table 7 Safety Monitoring Rules for Treatment-emergent Elevated ALT and/or Bilirubin**

Treatment-emergent ALT	Treatment-emergent total bilirubin	Treatment-emergent symptoms	Action

Normal baseline            ALT <math>\geq 5 \times</math> ULN
 
Elevated baselinea:            ALT <math>\geq 2 \times</math> baseline or  <math>\geq 300</math> U/L (whichever occurs first)
	Normal or elevated	Severe fatigue, nausea, vomiting, right upper quadrant pain or Immunologic symptoms Rash Eosinophilia $>5\%$	Interrupt investigational product b Initiate close monitoring and workup for competing etiologies. Investigational product can be restarted only if another etiology is identified and liver enzymes return to baseline. Testing for hepatitis A, B, and/or C infection may be warranted. Note: Subjects who entered the induction study (SHP647-301 or SHP647-302) with HBcAb with or without HBsAb would need evaluation with HBV DNA to rule out HBV reactivation. c

ALP=alkaline phosphatase; ALT=alanine aminotransferase; AST=aspartate aminotransferase; HBcAb=hepatitis B core antibody; HBsAb=hepatitis B surface antibody; HBV=hepatitis B virus; TBL=total bilirubin; ULN=upper limit of normal

a Elevated baseline ALT defined as ALT  $\geq 1.5 \times$  ULN.

b Confirmatory repeat liver-related blood tests should be performed within 2-3 days before the investigational product is interrupted.

c If HBV DNA positive, antivirals would need to be started as soon as possible.

Source: Adapted from [Chalasan and Regev, 2016](#).

## **9. DATA MANAGEMENT AND STATISTICAL METHODS**

### **9.1 Data Collection**

The investigators' authorized site personnel must enter the information required by the protocol in the eCRF. A study monitor will visit each site in accordance with the monitoring plan and review the eCRF data against the source data for completeness and accuracy. Discrepancies between source data and data entered in the eCRF will be addressed by qualified site personnel. When a data discrepancy warrants correction, the correction will be made by authorized site personnel. Data collection procedures will be discussed with the site at the site initiation visit and/or at the investigator's meeting. It is expected that site personnel will complete the eCRF entry within approximately 3 business days of the subject's visit.

### **9.2 Clinical Data Management**

Data are to be entered into a clinical database as specified in the CRO's data management plan. Quality control and data validation procedures are applied to ensure the validity and accuracy of the clinical database.

Data are to be reviewed and checked for omissions, errors, and values requiring further clarification using computerized and manual procedures. Data queries requiring clarification are to be communicated to the site for resolution. Only authorized personnel will make corrections to the clinical database, and all corrections are documented in an auditable manner.

### **9.3 Data Handling Considerations**

Prior to the unblinding described in Section 6.2.4, data that may potentially unblind the treatment assignment (ie, investigational product serum concentrations, antibodies to investigational product, treatment allocation, and investigational product preparation/accountability data) will be handled with special care during the data cleaning and review process. These data will be handled in such a way that, before unblinding, any data that may unblind study team personnel will be presented as blinded information or otherwise will not be made available. If applicable, unblinded data may be made available to quality assurance representatives for the purposes of conducting independent drug audits.

#### 9.4 Statistical Analysis Process

The study will be analyzed by the sponsor or its agent.

The statistical analysis plan (SAP) will provide the statistical methods and definitions for the analysis of the efficacy and safety data, as well as describe the approaches to be taken for summarizing other study information such as subject disposition, demographics and baseline characteristics, investigational product exposure, and prior and concomitant medications. The SAP will also include a description of how missing, unused and spurious data will be addressed. The SAP will be finalized before unblinding to preserve the integrity of the statistical analysis and study conclusions.

All statistical analyses will be performed using SAS® Version 9.3 or higher (SAS Institute, Cary, NC, US).

Unless otherwise specified, summary tabulations will be presented by treatment group. All data listings will be sorted by treatment group, site, and subject number, and will include the subject's age, sex, and race.

For categorical variables, the number and percentage of subjects within each category (with a category for missing data as needed) of the parameter will be presented. For continuous variables, the number of subjects, mean, median, standard deviation, minimum, and maximum values will be presented.

Note: The overall impact of COVID-19 (or other similar pandemic) on data analyses is unknown at the time of the writing of this amendment; details on changes to any analyses or any additional analyses to evaluate the impact of COVID-19 (or other similar pandemic) on the study objectives will be described in the SAP.

